5.2 Handling of Study Interventions

The FDA-approved vaccines to be administered in this study, Pneumovax-23 and Prevnar-13, will be ordered and received by the Research Pharmacist at UConn Health, per University policy. Once the study has IRB approval and is ready to initiate, the research pharmacist will dispense all vaccine doses to the UConn Center for Aging research team where they will be stored during the active study period. The UConn Center on Aging Clinical Research unit has a medication refrigerator in which vaccines will be stored until use. Temperature logs will be kept for the refrigerator 24 hours per day, 7 days per week, using an electronic temperature monitoring device that records temperature every 15 minutes. Logs will be downloaded weekly during the study period with a copy of the log added to the study regulatory binder.

Vaccinations will be given by an RN at Visit 2. Randomization and Vaccination Forms will be used by the study team to record the sequential randomization number assigned to each participant when eligibility was confirmed, the participant ID (PID) for the study, the vaccine that was administered, expiration date of the dose, date of administration and the signature of the nurse that administered the vaccine. The sticker from the dose packaging will be added to the form.

Participants will be informed of the vaccine that was administered to them and will be provided with information about the vaccine as provided by the manufacturer. Pneumovax 23 has an FDA- approved Patient Product Information Sheet that will be provided to participants receiving Pneumovax 23. Participants that receive Prevnar 13 will receive a Fact Sheet about the vaccine prepared by Pfizer (Appendix 1). Participants will also receive a handout from CDC about the vaccine that was administered.

Each participant will be given a Documentation of Pneumococcal Vaccine Administration as a record of their vaccination to share with their physician.

-to next page for study schema-

6 STUDY PROCEDURES

6.1 Schedule of Events

Intervention	Day -7 Visit 1	Day 0 Visit 2	Day 1 Visit 3	Day 10 (± 1 d) Visit 4	Day 28 (± 3 d) Visit 5	Day 60 (± 5 d) Visit 6	Day 365-730 Optional Visit 7
Informed Consent Prior to study activities	X						
Screening Form	X						X
Vital Signs (blood pressure, heart rate, temperature)	X	X	X	X	X	X	X
Body weight	X				X	X	X
Height	X						
Medical History	X						
Medical History update					X	X	X
Concomitant Medications	X				X	X	X
Adverse Events	X	X	X	X	X	X	X
Peripheral blood specimen (50 mL)	X		X	X	X	X	X
Peripheral blood specimen (10 mL) (pre-vaccination)		X					
Vaccination with Prevnar 13 or Pneumovax 23 by randomized assignment		X					
Vaccination with Prevnar 13 or Pneumovax 23, Other than received at V1							X

(optional)								
------------	--	--	--	--	--	--	--	--

6.2 Description of Study Visits

Visit 1: Day -7. Approximate visit time = 1 hour.

Consent Procedure

At the conclusion of the preliminary phone screening, study personnel briefly explain the study and provide potential subjects a copy of the approved ICF for review, in advance, whenever possible. Subjects will be encouraged to discuss study participation with family members and/or trusted advisors. At Visit 1, the ICF will be reviewed with the subject section by section by a qualified member of the study team in a private area. Subjects will be given the opportunity to ask questions and to have them fully answered. Subjects who elect to enroll will sign and date the consent form. The member of the study team conducting the informed consent discussion will also sign the ICF. A copy of the ICF signed by the consenter and the subject will be provided to the subject. This process will be documented by the Documentation of Consent Form that will be stored in the research record under a unique participant identifier (PID). The original signed ICF will be stored separately from the research record and with other study documents that contain personal identifiers (HIPAA Authorization, W-9, or other).

The HIPAA Authorization form will be provided to the participant to review and sign to authorize the use and disclosure of their Protected Health Information collected for use in this study.

Enrollment

- The participant is considered enrolled and receives a Participant ID (PID) number in the study once the ICF has been signed.

Screening

After informed consent, the following study activities will be performed:

- Medical History Form
- Recording of Concomitant Medications
- Taking and recording of body temperature (°F) oral or ear
- Screening Form completed with subject by interview
- Once all inclusion and exclusion criteria have been reviewed and the subject has been determined to have met all eligibility criteria, the subject proceeds to randomization.

Randomization

- If the subject does not meet all eligibility criteria during the screening process, the subject is not randomized to vaccine and is not assigned a randomization number.
- If study entry is deferred to meet a 28 day interval from receipt of Zostavax, blood will not be drawn at this time. Visit 1 procedures (other than Consent) will be rescheduled and performed when the 28 day interval between vaccinations has been met.
- Once the subject has met all eligibility criteria, they are assigned the next available sequential randomization number on the Randomization Log. The PID is entered in

the space next to the number on the Randomization Log and the Randomization number is entered on the Randomization and Vaccination Form for this PID to be used at Visit 2.

- Visit 2 is scheduled 7 days from Visit 1. There is no window for sample collections in this study.

Baseline measures

- Vital signs (blood pressure, heart rate, and respiration rate), weight and height are recorded.
- **Blood draw of 50 mL:** Blood will be collected peripherally by phlebotomy by qualified research staff using best practices. The tubes will be labeled with PID, Visit number and date of collection. Fifty (50) mL will be drawn and securely transferred to JAX-GM for processing and analysis. Three (3) mL will be sent by JAX-GM to Quest Diagnostics Laboratory or to another JAX campus for a complete blood count (CBC) with differential testing for research purposes only. The results of the CBC blood test will be coded with the PID number only and will not be placed in medical records. Results will be sent back to Jackson Laboratory for use in research testing. Results will not be shared with research participants, however, if the study doctor feels that blood sample shows abnormalities during research testing, he may contact participant and advise them to follow-up with their personal physician.

Visit 2: Day 0: Vaccination Visit. Approximate visit time = 15-30 minutes.

At Visit 2, the following procedures will be performed:

Body Temperature and Blood Draw

- Taking and recording of body temperature °F (oral or ear)
If the participant has a body temperature of 100.5°F (38° C) or greater, Visit 2 will be deferred and rescheduled for a minimum of 3 days in the future.

A deferral of vaccination due to fever will not require an additional Visit 1 blood draw 7 days in advance of vaccination as long as vaccination occurs within 14 days of the original Visit 1 blood draw.

Participants with a temperature below 100.5°F will proceed to blood draw.

- **Blood draw of 10 mL:** Blood will be collected peripherally by phlebotomy by qualified research staff prior to vaccination. The tube will be labeled with PID, Visit number and date of collection and will be securely transferred to JAX-GM for processing and analysis.
- The research nurse reviews the Randomization and Vaccination form and identifies the assigned vaccine from the Randomization Plan for the randomization number.
- The subject is informed of the randomized vaccine assignment and given information about the vaccine.

Data Collection

- Adverse events

- Concomitant medication use

Vaccination

- The research nurse obtains one dose of the assigned vaccine from the refrigerator and prepares the dose per the package insert.
- The vaccine dose label (sticker) is placed in the designated area of the Visit 2 Source Document Form.
- The area of the deltoid where the vaccine will be injected is wiped with alcohol
- The vaccine is injected intramuscularly in the deltoid by the RN.

The participant must remain at the clinic for 30 minutes after vaccine administration to be monitored for life-threatening allergic reactions. Visits are scheduled for study visits 3-6. There is no visit window for follow-up visits. Visits must be performed on the day indicated. The nurse will discharge the participant after 30 minutes has elapsed.

Visit 3: Day 1: Follow-up visit. Approximate visit time = 15 minutes.

Weight, Blood pressure, heart rate, temperature: taken and recorded on source document.

Data Collection

- Adverse events
- Concomitant medication use

Blood Draw

- **Blood draw of 50 mL:** Blood will be collected peripherally by phlebotomy by qualified research staff prior to vaccination. The tube will be labeled with PID, Visit number and date of collection. The sample will be securely transferred to JAX-GM for processing and analysis following the study visit.

Visit 4: Day 10 (\pm 1 day) : Follow-up visit. Approximate visit time = 15 minutes.

Weight, Blood pressure, heart rate, temperature: taken and recorded on source document.

Data Collection

- Adverse events
- Concomitant medication use

Blood Draw

- **Blood draw of 50 mL:** Blood will be collected peripherally by phlebotomy by qualified research staff prior to vaccination. The tube will be labeled with PID, Visit number and date of collection. The sample will be securely transferred to JAX-GM for processing and analysis following the study visit.

Visit 5: Day 28 (\pm 3 days): Follow-up visit. Approximate visit time = 15 minutes.

Weight, Blood pressure, heart rate, temperature: taken and recorded on source document.

Data Collection

- Adverse events
- Concomitant medication use
- Medical History Review and update

Blood Draw

- **Blood draw of 50 mL:** Blood will be collected peripherally by phlebotomy by qualified research staff using best practices. The tubes will be labeled with PID, Visit number and date of collection. Fifty (50) mL will be drawn and securely transferred to JAX-GM for processing and analysis. Three (3) mL will be sent by JAX-GM to Quest Diagnostics Laboratory or to another JAX campus for a complete blood count (CBC) with differential testing for research purposes only. The results of the CBC blood test will be coded with the PID number only and will not be placed in medical records. Results will be sent back to Jackson Laboratory for use in research. Results will not be shared with research participants, however, if the study doctor feels that blood sample shows abnormalities during research testing, he may contact participant and advise them to follow-up with their personal physician.

Planning for Optional Visit 7 at Visit 6 or earlier:

To receive vaccination with the other pneumococcal vaccine (Prevnar or Pneumovax) that was not randomly assigned and administered at Visit 2, 1-2 years after administration of randomly assigned vaccine at Visit 2.

- Discuss the option to schedule vaccination with the other vaccine one-two years from when the randomly assigned vaccine was administered.
- Ask the participant if they are interested in receiving the second vaccine at one-two years free of charge and document their choice on the Visit 7 opt-in form.

Participants interested in second vaccination:

- Document participant choice on Visit 7 opt-in form.
- Schedule the visit 365-730 days from date of Visit 2 vaccination.
- Confirm with the participant that they agree to be contacted to be reminded of this visit two weeks prior and again the day before planned Visit 7.
- Participant may change their mind about receiving second vaccine at any time.

Participants not interested in second vaccination:

- Document participant choice on the Visit 7 opt-in form.
- Study participation ends at Visit 6. Complete End of Study form.
- Participants can change their mind before the two-year anniversary of Visit 2 and decide that they would like to receive the other pneumococcal vaccine free of charge. Participants will be instructed to contact the study team if they would like to receive the second vaccine.

Visit 6: Day 60 (\pm 5 days) : Follow-up visit. Approximate visit time = 15 minutes

Weight, Blood pressure, heart rate, temperature: taken and recorded on source document.

Data Collection

- Adverse events
- Concomitant medication use
- Medical History Review and update

Blood Draw

- **Blood draw of 50 mL:** Blood will be collected peripherally by phlebotomy by qualified research staff prior to vaccination. The tube will be labeled with PID, Visit number and date of collection. The sample will be securely transferred to JAX for processing and

analysis following the study visit.

Visit 7: Day 365-730 (optional) Second vaccine visit Approximate visit time = 30 minutes.

Data Collection

- Adverse events
- Concomitant medication use
- Medical History Review and update
- Screening Form for Visit 7 Vaccination
- Body Temperature. Temperature is taken and recorded on the Visit 7 CRF. If the participant has a body temperature of 100.5°F (38° C) or greater, Visit 7 will be deferred and rescheduled for a minimum of 3 days in the future.

Body Temperature and Blood Draw

- Body Temperature. Temperature is taken and recorded on the Visit 7 CRF. If the participant has a body temperature of 100.5°F (38° C) or greater, Visit 7 will be deferred and rescheduled for a minimum of 3 days in the future. Participants with a temperature below 100.5°F (38° C) will proceed to blood draw.
- **Blood draw of 50 mL:** Blood will be collected peripherally by phlebotomy by qualified research staff prior to vaccination. The tube will be labeled with PID, Visit number and date of collection. The sample will be securely transferred to JAX-GM for processing and analysis following the study visit.

Vaccination

- The research nurse reviews the Randomization and Vaccination form and identifies the vaccine administered at Visit 2. The other vaccine will be administered at Visit 7. (Prevnar at V2 receives Pneumovax at V7, Pneumovax at V2 receives Prevnar at V7).
- The research nurse obtains one dose of the Visit 7 vaccine from the refrigerator and prepares the dose per the package insert.
- The vaccine dose label (sticker) is placed in the designated area of the Vaccination Form for Visit 7.
- The area of the deltoid where the vaccine will be injected is wiped with alcohol
- The vaccine is injected intramuscularly in the deltoid by the RN.
- The participant is given the patient information handout for the vaccine received.
- The RN completes and signs the Vaccination Form for Visit 7.

The participant must remain at the clinic for 30 minutes after vaccine administration to be monitored for life-threatening allergic reactions. The nurse will discharge the participant after 30 minutes has elapsed and note the time on the Vaccination Form for Visit 7.

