Protection against Risk from Blood Draw:

Blood will be drawn peripherally via venipuncture at all visits. The volume drawn will be 50 mL at Visits 1, 3, 4, 5, 6 & (optional visit) 7 and 10 mL at Visit 2. Blood will be drawn by

experienced, trained research staff in a clinic setting on a hospital campus. The area where the needle will be inserted will be wiped with alcohol before and after the draw. A band-aid will be placed over the site. Emergency treatment is accessible on campus for any severe complications from blood draw.

Protection from Risk from Information on CMV Serology and Infection:

Information about CMV infection will not be shared with individual subjects or their physicians. In addition to the importance of maintaining the “firewall” between our clinical and genomic studies, there is at this time no evidence that a positive CMV serology should result in any specific course of action on the part of the patient or his/her physician. As a result, a decision to share such information would only result in unnecessary anxiety and confusion.

Protection against Risk of Vaccination with Prevnar 13:

A detailed medical history questionnaire will be completed by the participant and reviewed by a qualified member of the study team to identify contraindications to vaccination and to determine study eligibility. For eligible participants, assigned vaccine will be administered by a Registered Nurse as a single dose, given intramuscularly in the deltoid. Participants will be required to remain on site for 30 minutes after vaccine administration so that they can be monitored for adverse events.

Protection against Risk of Vaccination with Pneumovax 23:

In addition to protections listed under vaccination with Prevnar 13, participants will be asked about recent vaccination with Zostavax for shingles within the prior 28 days from date of planned vaccination or if they are planning to receive Zostavax in the 28 days following. In order to optimize response to all vaccines, study entry may be delayed to allow 28 days between vaccine administrations. If study entry is delayed, eligibility criteria will be reviewed and confirmed prior to randomization.

Protection against Risk from optional second vaccination one to two years after initial vaccine (Visit 7):

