7.3 Adverse Events and Serious Adverse Events

An **adverse event (AE)** is defined as any unfavorable and unintended diagnosis, symptom, sign, syndrome or disease which either occurs during the study, having been absent at baseline, or if present at baseline, appears to worsen. Adverse events will be collected and recorded at each visit regardless of their relationship to the study intervention or to study participation.

A **serious adverse event (SAE)** is defined as any untoward medical occurrence that results in death, is life threatening, requires inpatient hospitalization or prolongation of existing hospitalization, results in persistent or significant disability/incapacity, or is a congenital anomaly.

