7.4 Reporting Procedures

The Clinical Principal Investigator will review all AEs and SAEs to assess causality. The IRB requires reporting of unexpected adverse events that may represent an unanticipated problem involving risks to subjects or others (UPIRSO). Such events are to be reported to UConn Health IRB using the Problem Report Form within the IRIS electronic IRB submission system.

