7.6 Data and Safety Monitoring

Data and Safety Monitoring Plan

The Data & Safety Monitoring Plan for this study describes the components of the study that will be monitored by the PI, study coordinator and data manager once annually. Recruitment, drop outs, adverse events, unanticipated problems, data integrity and confidentiality, participant privacy and the general conduct of the study will be reviewed. Minutes of the annual DSMP review will be kept in the regulatory binder and provided to IRB at study continuation. The vaccines given in this study are given at the dose, via the route and in the population for which they are approved by FDA, and study samples are limited to peripheral blood draws in healthy older adults, thus this study poses minimal risk to research subjects. As a result, a Data Safety Monitoring Board (DSMB) is not indicated. Nevertheless, robust procedures are in place to ensure confidentiality of research data.

Procedures in place to ensure confidentiality of research data are as follows:

1. Only authorized individuals have access to any data, used or stored (via electronic format or as hard copy records). Only designated research staff and investigators will be granted access.

2. Logon IDs and passwords for access to the UConn Center on Aging shared network drive and the University's online resources are initially assigned by the Information Technology Department (IT).
3. All data (clinical, recruitment and schedule-based) are stored in password-protected databases on the secured network drive. Only approved personnel have access to these databases and passwords.
4. All data collected on data forms are stored in locked drawers located in the Center on Aging research facility for scanning and verification purposes. Files are stored in locked cabinets in rooms that are locked when not in use. All data are backed up on the shared network drive for UCHC.

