9 DATA COLLECTION AND MANAGEMENT

Data Collected from Human Subjects Specifically for Research Purposes

Medical and medication history provided by the participant: Prior to the first collection of blood at Visit 1, individuals who have consented to participate in the study will be asked to fill out a detailed health history questionnaire with past and current medical conditions with date of diagnosis, including current and prior medication use, and vaccine history.

At all visits, participants will be asked about recent health history (e.g., colds, flu, pneumonia-like symptoms, hospitalizations, infections) and concomitant medication use since the previous review.

Vital signs (blood pressure, heart rate, temperature) and adverse events will be collected by a qualified member of the study team at each visit.

Height at Visit 1 only, weight at all visits.

Participant Identification (PID) number:

A unique participant identifier (PID) not derived from any patient identifiers will be assigned to each participant once written informed consent for study participation has been obtained. All clinical data will be linked to the PID in the database. Participant names or other personal identifiers will not be included in the study data set; all data will be identified only by PID.

Access to individually identifiable private information about human subjects

Access to clinical research records and identifiable study data will be restricted to the study team involved in the conduct of the clinical protocol. Coded clinical data will be provided to the JAX-GM laboratory staff for analysis linked with study samples by the PID. HIPAA personal identifiers will not be included in the clinical dataset provided to JAX-GM for use in analysis. The key linking the PID to participant identifiers will be stored separately and securely from the research records at the UConn Center on Aging. The code key will not be provided to the JAX investigator or staff at any time. JAX Lab staff will have access to coded samples and data only. [name], as a co-investigator on the clinical protocol may be present at clinical team meetings when identifiable information is present. He will not record or disclose participant identifiers and he will not receive the code key at any time.

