This form is completed at any time during study participation but must be completed before the end of Visit 6. The participant will indicate their intention to receive the second vaccine (not administered at Visit 2) at the optional Visit 7 as described in study procedures section or will decline the optional visit and second vaccine. The participant will sign and date the form and will be given a copy of the signed form for their records. This form will be stored with the ICF and HIPAA since it has a signature. Visit 7 will be scheduled for participants that choose to attend the optional Visit 7.

Visit 6 Source Documentation Form

This form captures members of the study team that collected data at this visit, vital signs and

blood draw documentation. Completion of Visit 7 Opt-in form is recorded and the selection of the participant made on the form.

Visit 7 (optional visit) Procedures Documentation Form:

- This form is a checklist for Visit 7 procedures for participants that opt for a second vaccination.
- **Vaccination administration detail for Visit 7:**
The research nurse will identify the original assigned vaccine and the other vaccine to be given at Visit 7 on this form. The sticker from the vaccine dose will be placed on the form. The time and date of vaccine administration and confirmation of the 30 minute post-vaccine observation period with time of dismissal will be recorded by the research RN.

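### No planned collection of adverse events that begin after the 30-minute wait following the optional second vaccine at Visit 7

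*Combined protocol and SAP*

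**What the plan says.** Two sections tie adverse-event collection to visits. Section 7.3 states: "Adverse events will be collected and recorded at each visit regardless of their relationship to the study intervention or to study participation". Section 9 says that "adverse events will be collected by a qualified member of the study team at each visit". The protocol describes no diary, telephone call or other route between visits.

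In the schedule of events (6.1), optional Visit 7 is the last column. In 6.2, its adverse-event entry appears under data collection, ahead of the blood draw and the injection. The visit then ends as follows: "The nurse will discharge the participant after 30 minutes has elapsed and note the time on the Vaccination Form for Visit 7". The Visit 7 form in 9.1 ends at the same point: "The time and date of vaccine administration and confirmation of the 30 minute post-vaccine observation period with time of dismissal will be recorded".

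The contacts planned around Visit 7 all come before it. Section 6.2 asks opt-in participants to confirm that they "agree to be contacted to be reminded of this visit two weeks prior and again the day before planned Visit 7". For the second dose, Section 7.2 lists a history review and an eligibility check, both before the injection.

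**The concern.** The second dose is a study procedure. The study supplies it, schedules it and has its own nurse give it, and Section 7.1 gives it a separate risk paragraph. That paragraph discusses antibody levels for the two vaccine sequences and gives no reaction data for either.

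Two safety processes depend on adverse events reaching the team. Section 7.4 says: "The Clinical Principal Investigator will review all AEs and SAEs to assess causality". Of the annual review, Section 7.6 says: "Recruitment, drop outs, adverse events, unanticipated problems, data integrity and confidentiality, participant privacy and the general conduct of the study will be reviewed". For the second dose, the protocol gives both processes no planned source of information beyond the first 30 minutes.

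The events at stake are serious or unexpected reactions with later onset. Expected label reactions, such as a sore arm, matter less here because they would not normally meet the unanticipated-problem test in 9.5.

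**Working it through.** The check compares planned collection after each dose and then counts the doses affected. The plan states no figure of its own to reproduce.

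**Planned collection after each dose**

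| | First dose (Visit 2, Day 0) | Second dose (Visit 7, Day 365 to 730) |
|---|---|---|
| On-site observation (6.2) | 30 minutes | 30 minutes |
| Later visits recording adverse events (6.1, 6.2) | Days 1, 10, 28 and 60: 4 visits | 0 |
| Other planned contacts after the dose | None stated | None stated |
| End of planned coverage | Day 60 ± 5: 60 − 5 = 55 to 60 + 5 = 65 days | 30 minutes |

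The 30-minute stay does count as monitoring. Section 6.2 directs it at life-threatening allergic reactions. Section 7.2, describing the assigned vaccine, is broader: participants are "required to remain on site for 30 minutes after vaccine administration so that they can be monitored for adverse events". The gap is therefore limited to events that begin after discharge.

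**Whether another section closes it**

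- Sections 7.4 (causality review), 7.5 (treatment), 7.6 (annual review) and 9.5 (unanticipated problems) act on events the team already knows about. None says how the team would learn of one after Visit 7.
- In 6.2, the instruction that participants contact the team is for those who first decline the second vaccine and later want it. It does not concern reactions.
- Section 7.3 defines an adverse event as something arising during the study. Section 6.2 states when participation ends only for those who decline Visit 7 (at Visit 6). For those who opt in, the text does not settle whether an event two days after the second dose falls within the study.

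**Doses affected**

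The documents give no opt-in rate, so a range is assumed. With 40 first doses and opt-in proportion p:

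- second doses = 40 × p
- share of all study doses = 40p / (40 + 40p)

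| Assumed p | Second doses | Share of all doses |
|---|---|---|
| 25% | 10 | 10/50 = 20% |
| 50% | 20 | 20/60 = 33% |
| 100% | 40 | 40/80 = 50% |

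The documents give no rate for serious or unexpected late reactions, so the number of missed events is not estimated.

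**The case against.** The strongest counter-argument is that this is a preference about a low-risk, licensed product. Both vaccines are given at the approved dose and route. Section 7.1 regards the conjugate-then-polysaccharide sequence at one year as carrying the risk of routine care, and the reverse order is within the CDC guidance summarised in Section 2.1 for adults 65 and older. No aim or analysis in Section 8 has a safety endpoint. The Day 1 to Day 60 visits are timed for immunology sampling (1.1), so four visits against none is not a departure from a safety standard that the protocol sets. A spontaneous report after Visit 7 would still be handled under 7.4 and 9.5, and the consent form or handout may tell participants to call.

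Much of this stands, and it keeps the point minor. The comparison with the first dose describes coverage and sets no benchmark. The contact would also say little about rates: with no events observed, the one-sided 95% upper bound, 1 − 0.05^(1/n), is about 7% for n = 40 and 26% for n = 10. Its value lies in following up individual participants.

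The objection does not remove the gap. Section 7.6 uses minimal risk to justify having no data safety monitoring board. It does not waive adverse-event collection, and the same section requires adverse events to be reviewed. A route for handling spontaneous reports is not a plan to ask. The unseen consent text limits the claim to what the protocol says, and on that basis the claim holds.

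**Conclusion.** The concern holds as a minor design point. As written, the protocol plans 30 minutes of observation after the second study-supplied dose and no adverse-event collection after that, against four visits over 55 to 65 days after the first dose. The absence of a planned contact is read directly from the text and needs no assumption. The count of 10 to 40 second doses, or 20% to 50% of all doses, rests on an assumed opt-in of 25% to 100% and on all 40 participants receiving the first dose. It measures exposure to the gap and does not estimate harm. No antibody, transcriptomic or epigenetic result is affected.

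**What to change.** Add one adverse-event and serious-adverse-event contact after Visit 7 to Sections 6.1 and 6.2, for example a telephone call at about 10 days, and add a field for it to the Visit 7 form in 9.1. The 10-day interval matches Visit 4 and is chosen for convenience; the documents do not supply an interval based on reaction onset. It would also help to state that participation for those who opt in ends at this contact.

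The cost is protocol and form wording, IRB approval of the modification (10.1), and one short call per opt-in participant: 10 to 40 calls at the assumed uptake. No new staff, blood draw or clinical procedure is needed. The contact agreement in 6.2 covers only the two reminders before the visit, so its wording should be extended, and participants who have already opted in may need to agree to the call. Some calls will go unanswered.
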